#### 1.0 **SUMMARY:**

Cumulative epidemiological evidence indicates that physical inactivity confers risk for cardiovascular disease (CVD), and that current physical activity (PA) guidelines (prescribed at >150 minutes per week of moderate to vigorous intensity aerobic PA) can reduce CVD morbidity and mortality. The biological and behavioral pathways by which PA may reduce CVD risk is still unclear. In line with the P01 focus on neurobiology of CVD risk, we are conducting a 12-month PA intervention with 150 midlife and inactive adults randomized to: (1) 150 minutes per week of moderate to vigorous intensity exercise (i.e., brisk walking; N=75); or (2) a PA and health information group where we will provide cardiovascular information and active daily monitoring (N=75). A comprehensive battery of cardiorespiratory fitness (CRF), cardiovascular health, physiological biomarkers such as endothelial function, and magnetic resonance imaging (MRI) measures will be assessed at baseline, after 6-months, and again after completion of the intervention.

We have assembled a highly creative, productive, and interdisciplinary team with a long history of collaboration and experience conducting exercise interventions to test the following aims:

### **Aim 1**: To determine the Neurobiology of Exercise and Biological CVD risk factors:

- (1A) *Body-to-Brain hypothesis*: Exercise-induced changes in peripheral markers of CVD risk (i.e., insulin resistance, pulse wave velocity, CRF, oxidative stress, biomarkers of endothelial function) will precede and partly explain (statistically mediate) exercise-induced changes in functional and structural features of some areas within visceral control circuits (prefrontal cortex [PFC], anterior cingulate cortex [ACC], insula, hippocampus, and amygdala).
- (1B) Brain-to-Body hypothesis: Exercise-induced changes in functional and structural features of some areas within visceral control circuits precede and partly explain (statistically mediate) consequent changes in peripheral autonomic and neuroendocrine mediators of CVD risk that are under neural regulation, including baroreflex sensitivity, heart rate variability, glucocorticoid control.

## **Aim 2:** To determine the Neurobiology of Exercise and Stress- and Affect-related CVD risk factors:

- (2A) Stress-related parameters of CVD risk: Exercise will induce changes in visceral control areas engaged by an fMRI stress battery, and these changes will partly explain exercise-induced reductions in cardiovascular stress reactivity in daily life.
- (2B) Affect-related parameters of CVD risk: Exercise will induce changes in visceral control areas engaged by an fMRI emotion processing and regulation paradigm in synergy with Project 1 (P1), and these changes will partly explain exercise-induced improvements in positive and negative affect measured in daily life by EMA and by conventional self-report instruments in synergy with Project 2 (P2).

#### 1.1 BACKGROUND AND RATIONALE:

PA is one of the most critical behaviors to reduce risk for many chronic diseases, including some cancers (e.g., breast cancer), cardiometabolic conditions (e.g., Type II diabetes), and atherosclerotic cardiovascular disease (CVD). Moreover, PA has beneficial effects on a range of proximal mediators and markers of chronic disease risk especially CVD risk. These include blood pressure (BP), cardiac autonomic control, inflammation, glucose regulation, adiposity, and lipid levels. In patient samples, clinical trials show that PA accelerates recovery from myocardial infarction, coronary bypass surgery and congestive heart failure, improves quality-of-life, and reduces risk for new CVD events and all-cause mortality. Further, cardiac patients who improve their fitness show a 20% reduced mortality rate over an 11-year follow-up period. Based on an expansive body of evidence, the American Heart Association (AHA) has identified CRF as an important 'vital sign', and it has recommended more frequent assessments and management of fitness by health professionals. Finally, physical *inactivity* is estimated to account for >350,000 deaths per year in the USA alone, with an additional 3.2 million annual deaths globally. In view of clear scientific evidence on PA and health, many international organizations have nearly identical recommendations for people to engage in PA. The most recent were established in 2018, advising >150 min of moderate intensity exercise, or at least 75 min of vigorous exercise, per week to improve cardiovascular health and to reduce risks for premature mortality. Less widely appreciated by health care professionals, the public, and policy makers are the broad benefits of PA on the brain. These benefits translate into brain-based improvements in cognitive, affective, stress-buffering, and self-regulatory behaviors . Indeed, substantial human and animal evidence shows that the brain exhibits appreciable structural and functional plasticity (i.e., change) from PA. As a result of this evidence, many organizations that influence public policy have developed campaigns to educate the public and health care professionals on the brain benefits of PA. For example, the NHLBI and AHA note mood improvements and reductions in psychological distress as established benefits of engaging in PA . In support of these health campaigns, Barnes & Yaffe further reported that >1.1 million Alzheimer's cases in the USA are potentially attributable to physical inactivity. Noteworthy here is that Alzheimer's and other forms of dementia are highly co-morbid with CVD, and they are often predicted by CVD risk factors that are affected by PA (e.g., hypertension). Moreover, exercise reduces aspects of negative affect and depressive symptoms that associate with CVD risk. Finally, there is preliminary evidence to suggest stress-buffering effects of PA and cardiorespiratory fitness at the level of physiology and behavior, which may define additional pathways to reduce CVD risk. What is not known, however, is whether the beneficial effects of exercise on the brain extend beyond emergent cognitive, affective, and stress-buffering processes to also include beneficial effects on physiological and systemic mediators of CVD risk that are regulated by the brain. If so, such effects may help to more precisely define and refine novel and brain-based targets for intervention and prevention efforts.

#### 1.2 **INNOVATION:**

We have assembled a productive team with a history of collaboration in exercise interventions. eBACH questions are unique in the field, potentially transformative, and relevant to both scientists and health professionals.

- **Body-to-brain pathways linking physiology and exercise.** For the first time, we will test whether exercise-induced changes in peripheral markers of CVD risk explain changes in brain plasticity.
- Brain-to-body pathways linking exercise and physiology. We will test the novel
  hypothesis that the effects of exercise on brain circuits supporting visceral control
  account for changes in autonomic, hemodynamic, and neuroendocrine mediators of
  CVD risk.
- Dense repeated measurement of exercise and neural-CVD risk associations. For the first time in a randomized exercise intervention, we will collect 3 measurement points of high-resolution neuroimaging data and peripheral mediators and markers of CVD risks. This allows us to more accurately model trajectories of change for both neuroimaging and CVD risk related measures, enabling us to move beyond traditional correlation, observational, and briefer wave assessments of these associations.
- Statistical modeling of exercise and CVD risk. We have the expertise to apply cutting-edge machine learning approaches to neuroimaging, behavioral, and peripheral biomarkers to develop a more comprehensive and realistic model of the associations between exercise and its associations with peripheral physiology, risk factors for CVD, and brain plasticity.
- Neurobiology of exercise and emotion and stress linked to CVD risk. We will
  examine how exercise alters stress physiology and affective CVD risk correlates via
  changes to brain circuits.

#### **1.3 PRELIMINARY DATA:**

- 1. Peripheral mediators and markers of CVD risk and PA: In the AHAB2 registry, we tested associations between markers and mediators of CVD risk and PA after control for age and sex. In AHAB2, energy expenditure (assessed over ~5 days by actigraphy) was negatively correlated with mean carotid intima-media thickness (p = 0.017, N = 437) and an aggregate metabolic risk score (p < 0.001, N = 414). Also, energy expenditure was positively correlated with an index of cardiac vagal control derived from high-frequency heart rate variability (HF-HRV) and root mean square of successive differences (RMSSD) measured during paced and unpaced breathing epochs (p < 0.001, N = 432). Moreover, greater energy expenditure correlated with lower interleukin 6 (IL-6) and C-reactive protein (CRP) (ps < 0.001, Ns = 453 and 454). The cardiac vagal control index also negatively correlated with IL-6 and CRP (p's < 0.005, Ns = 448 and 449). In line with our aims, energy expenditure was positively correlated with bilateral hippocampal volume after additional control for intra-cranial volume (ICV) (p = 0.024, N = 425). Finally, the cardiac vagal control index was positively correlated with volumes of the ACC, amygdala, and hippocampus (ps < 0.05). Implications for this project: These results show associations between PA and peripheral markers and mediators of CVD risk, and that these associations may be linked to markers of brain plasticity and health. What is unknown, and what is tested here, is whether such cross-sectional associations between CVD risk markers, PA, and brain health are causally linked in the context of an experimental manipulation of PA.
- 2. **PA**, **stress**, **and affect**: In brief, we replicate several observations from the literature on associations between PA and fitness with affect, and we provide the first

evidence that PA relates to blunted stressor-evoked BP reactivity in daily life. We also report the first associations to our knowledge on PA and individual differences in neural activity during the processing of negative emotional stimuli, as well as during the regulation of negative emotions. In aggregate, these initial findings support the integration of the fMRI stressor and emotion task batteries, as well as ambulatory (ABP) and ecological monetary assessment (EMA) methods.

3. Exercise and brain health: Our research group has published >170 papers on the effects of exercise and fitness on brain morphology, white matter integrity, resting state connectivity, and task-evoked functional MRI activity. But, none of these have specifically addressed the questions at issue here. Evidence from our work and others reliably demonstrates that PA and CRF are related to several metrics of brain health across the lifespan in clinical and healthy samples. For example, we found in children (N=35/group) that exercise is associated with changes in task-evoked fMRI, cerebral blood flow in the hippocampus, and increased hippocampal volume. Similar effects of exercise are seen in young adulthood and mid-life. For example, we found in a randomized trial of PA (N=125) in adults between 18-50 yrs that 12-months of PA increased cerebral blood flow in the ACC, insula, and PFC. Increases in hippocampal and PFC volume is also seen in young adults after 6-months of aerobic exercise. Similar positive effects of PA have been reported in mid-life adults with T1 diabetes, in multiple sclerosis patients, and in women with breast cancer. Positive effects of PA on brain health are often observed in late-life. For example, in 120 older adults (60-80 yrs; N=60/group), moderate intensity exercise increased hippocampal volume. Exercise also increased volume of the PFC and ACC in 59 (N=~28/group) older adults. In 879 older adults, greater energy expenditure was associated with greater volume of the hippocampus, ACC, and PFC. In addition to brain morphology, changes in CRF resulting from an exercise intervention were correlated with increased white matter integrity in PFC and temporal lobes in 70 older adults and also in two larger samples (N=113; N=154). Our results also extend to resting-state connectivity and taskevoked activation. For example, in 65 older adults exercise increased functional connectivity. Overall, this rapidly growing literature indicates that PA, CRF, and aerobic exercise in particular, is effective for improving several metrics of brain health in visceral control circuits and that these effects occur across the lifespan in diverse samples.

#### 1.4 STATISTICAL ANALYSIS:

**1.4.1. POWER:** Our proposed intervention is much larger and much longer than other similar well-controlled randomized PA interventions, especially those that include neuroimaging. Prior studies are typically <6 months in duration with N<25/group. Thus, our intervention with 3 measurement points (0, 6, 12 months) with N=150 (75/group) far exceeds other comparable studies in this area. Well-controlled RCTs typically have smaller sample sizes than traditional observational studies because of the increased power obtained through the within-subject analytical approach. Indeed, the number of assessments (450) is similar to that of Projects 1 and 2. Here we describe the statistical basis for our proposed design using an estimated sample size after 20% attrition (N=60/group). Brain

volumetrics: Our prior 6-12 month PA interventions in children, young adults, and older adults have used between 20^26 and 60^40 subjects per group with moderate-sized effects (Cohen's d) ranging between 0.30 and 0.50. Crosssectional research has supported these numbers with studies reporting significant effects of PA on brain volume with only 32 subjects and slightly larger effect sizes between 0.50 - 0.60. Even if we estimate a rather conservative effect size of 0.30, 60 participants per group is sufficient to detect differences in brain volume at 80% power. Diffusion imaging: Changes in white matter have been detected in PA interventions in as little as 6-months with only 50 subjects. In a 12-month exercise intervention, we found increased FA with only 35 subjects in each group with an estimated effect size of 0.70^28. Fewer results have been reported in midlife, but in children, effects of PA on white matter have been reported with N=25/group. Based on an estimated effect size of 0.75, we should have 90% power with 60 participants per group to test our main hypotheses as well as enough power for exploratory analyses. Connectivity: With only 65 people, we have shown that a 12-month exercise intervention is effective at enhancing functional connectivity in prefrontal-inhibitory networks. The difference between the groups for PFC connectivity was .15 with a standard deviation of .10 suggesting an effect size of 1.5 (Cohen's d). In young adults, we report similar effects with N=50 with increased functional connectivity between the anterior hippocampus and ACC. Therefore, similar to the effect sizes and power for the other neuroimaging measures, 60 participants per group should be sufficient for detecting changes as a function of the intervention with 95% power. Stress reactivity and affect: In preliminary data from the AHAB2 cohort, greater PA was associated with reduced daily life stress reactivity measured by strain (r=.23) and conflict (r=.25). In a 12-week exercise intervention in young adults with major depression scores on the Montgomery Asberg Depression Rating Scale significantly decreased from 21.8 to 4.25, and the magnitude of this decrease was correlated with increases in fitness (r=-.39). Based on these effect size data, 60 participants per group would provide us with >90% power to detect an effect on stress and affect measures. Thus, we estimate adequate power to test Aim 2. CVD markers: Prior randomized exercise interventions examining some of the same CVD risk markers proposed here (e.g., baroreflex sensitivity [BRS]) are typically between 4-52 weeks in duration with  $N=\sim10$  and  $150^{31}$ . Despite this heterogeneity, meta-analyses of exercise interventions show moderate-to-large effects on many of these outcomes (Cohen's d=.60). For example, a meta-analysis of 30 exercise interventions on multiple CVD risk markers reported an average 18 week duration with  $\sim 50$  subjects in each study ( $\sim 25/\text{group}$ ). In this metaanalysis, CRF increased by 3.04 mL/kg/min with a Cohen's d of 0.58. We expect larger effect sizes here because durations of ~1-year demonstrate larger changes in these metrics. Thus, based on prior studies and meta-analyses, we are sufficiently powered with N=150 to test for exercise-induced changes in CVD markers. Mediation: Using established empirical estimates of sample sizes needed for .80 power in bias-corrected bootstrapping analyses with moderate sized effects in both alpha and beta, it is estimated that 115 participants are needed. Thus, based on the above effect sizes for both brain and CVD markers, we are

sufficiently powered to test our hypotheses using structural equation modeling even after attrition. In sum, our planned sample size of 150 (N=75 per group) will be sufficient for allowing us to test our primary hypotheses.

**1.4.2. PRELIMINARY STEPS**: Prior to hypothesis testing, all data will be examined to determine: 1) frequency distributions for missing data and out-of-range values; 2) normality and internal consistency of subscales; and, 3) association between variables that may be highly correlated to guard against multicolinearity, which would inflate standard errors and make estimation

[figure not shown]

Figure 1. Diagram of exemplar full longitudinal mediational model. Paths involved in estimating longitudinal stability and residualized change are in black, paths involved in mediation are in red, and non-essential parameters are grayed out for legibility.

unstable. We will also examine the distribution of factors between groups to assess whether covariate-adjustment is required. Missing data: All outcomes will be tested using an intent-totreat (ITT) framework. Sensitivity will be explored using adherence to the intervention (e.g., per protocol). We will report reasons for dropouts and explore missing data mechanisms. To examine whether missingness is unrelated to other observed and unobserved measurements (missing completely at random, MCAR) or to the observed measurements only (missing at random, MAR), testing for completely random dropouts will be carried out. Additional sensitivity analyses test for informative dropouts. We will apply pattern-

mixture models by stratifying our data by dropout patterns and fitting separate regression models to strata.

1.4.3. PRIMARY OUTCOMES: Before testing the specific aims related to mediation we will test whether the intervention modifies proximal endpoints that will serve as the primary outcomes of the study. Thus, the primary endpoints will be 12-month change scores resulting from three different measurements: (1) hippocampal volume, (2) mean systolic blood pressure reactivity averaged from Stroop and Multi-Source Interference Task (MSIT) stressors during fMRI, and (3) heart rate variability. More specifically, we are predicting Time x Group interaction terms such that the exercise arm would change more than the control arm for these measures. Changes in scores of other measures including EMA-derived measures of daily life positive and negative affect, BRS, pulse wave velocity [PWV], vasodilation, CRF, resting state brain connectivity, and cortical thickness will be considered secondary and tertiary outcomes. Further, results from the structural equation modeling will be considered secondary outcomes, but will be testing the specific aims of the project.

We propose to test our primary hypotheses using a general linear mixed model (GLMM) approach because we will have three assessments for each of our measures over the course of the trial (baseline, 6-months, 12-months). The

GLMM model will include both random intercept and random slope for individual participants and a treatment-by-time interaction as a fixed effect. This technique will allow us to model the changes in the scores as a function of both time and group while also including other potentially confounding variables in the model. GLMM modeling of repeated assessments is a popular approach in clinical and longitudinal studies because it allows for random changes in measurement error and takes into account both within and between subject correlations and estimates the average growth curve across subjects and subject-specific growth curves.

**1.4.3 MEDIATION:** Aim 1 has two hypotheses, (a) to test whether the peripheral effects of exercise mediate brain effects, and (b) whether the effects of exercise on the brain mediate the beneficial effects of exercise on peripheral mediators of CVD risk. We propose to test these hypotheses using longitudinal mediation models in a structural equation modeling (SEM) framework. Aim 1A: In this model, the exercise groups (X) are proposed to influence visceral control circuits (Y) via changes in peripheral pathways (M) including insulin resistance, oxidative stress, endothelial dysfunction, and CRF. We will first examine whether brain or these peripheral CVD pathways can be summarized as latent variables to control for measurement error. When using latent variables, the modeling will proceed by first establishing well-fitting measurement models, and testing for measurement invariance across waves. To test the hypothesis proposed in Aim 1A, analyses will be conducted both on a voxel-wise basis (e.g., using the BRAVO Toolbox (https://sites.google.com/site/bravotoolbox/)) or using extracted data from SPM, FSL, or FreeSurfer, depending on the imaging modality and analysis. In the latter case, we will use a theory-driven approach by selecting values from anatomical or functionally-defined regions-of-interest (ROI) on visceral control regions. Each imaging modality will be analyzed in separate models unless we have a theoretical or empirical basis for including multiple imaging metrics in a single model. We will use standard cluster-based and FDR corrections for multiple comparisons for all voxel-wise analyses and the Brain Connectivity Toolbox for graph theory metrics (i.e., segregation). Although directional hypotheses have been posited for our mediation analyses, a more conservative significance will be set at .01 to limit inflation of type 1 error. Global and incremental model fit will be verified using multiple fit-indices (chi-square, RMSEA, CFI, TLI, SRMR). With three waves of data, we will use full longitudinal mediation to test our hypotheses. Full longitudinal mediation allows us to test the effect of initial standing on the hypothesized predictor (X – Exercise group) at T1 on change in the mediator (M – peripheral CVD markers) from T1 to T2, controlling for initial standing on M, and the effect of the mediator (M– peripheral CVD measures) at T2 on the change in the outcome (Y – change in brain measure) from T2 to T3, controlling for initial value of the outcome. Mediation will be tested by calculating the indirect effect of paths that are consistent with longitudinal mediation (i.e., paths a and b in Fig. 1). Here the estimate a\*b provides a measure of the longitudinal mediated effect because it represents the effect of X at T1 on residualized change in M (path a), and M at T2

on residualized change in Y (path b). Significance of the mediation (i.e., indirect) effect will be examined using techniques that account for non-normality in the parameter distribution, namely bias corrected bootstrapping-based approaches. A benefit of full longitudinal mediation models is that the direction of the paths can be reversed (Y->M->X) to test for the opposite causal direction, and bidirectional effects can similarly be tested. We will test for these possibilities by comparing models with paths reversed and allowing bi-directional effects. Finally, we aim to explore the role of other potential mediators (i.e., sleep) and moderators (e.g., gender) on the direction and strength of associations. Aim 1B: We will proceed with similar approaches described above for Aim 1A including using a voxel-wise approach and a theory-driven approach by selecting anatomical or functionallydefined ROIs on visceral control circuits or the white matter pathways that connect them. Importantly, there may be regional dissociations between the brain regions identified in Aim 1A and those identified in Aim 1B. Using voxel-wise analyses, we will be able to adjudicate the regional specificity or overlap between the regions identified in Aim 1A with those of Aim 1B. Using these procedures, we will also be able to determine the specificity of particular effects (e.g., regions associated with BRS but not with HRV) or differences across imaging metrics (e.g., differences of effect between functional connectivity, cortical thickness, white matter). With three waves of data, we will use full longitudinal mediation to test our hypotheses that X (Exercise group) influences BRS, HRV, and glucocorticoid control (Y) via its effects on brain plasticity on visceral control circuits (M). The description of the SEM modeling approach for Aim 1A will be applied to test mediation for Aim 1B. To test Aim 2A & B: The analytical plans for testing Aim 2A and 2B along the lines depicted in the heuristic model of Figure 1 will proceed like that described above for Aim 1A and B. That is, we will test how the effect of the hypothesized predictor (X – Exercise group) influences the change in the mediator (M – visceral control circuits), on stress reactivity and affect metrics that are measured in Projects 1-2 (e.g., EMA and ABP measures identical to those used in NOAH). Similar to Aim 1, we will be able to model opposite causal directions and bidirectional effects by reversing the paths in the model and will be able to determine specificity of particular effects (e.g., regions associated with emotion regulation, but not daily life stress reactivity) or differences across imaging metrics (e.g., differences of effect between functional connectivity, cortical thickness, white matter). As above, we will also test other potential mediators (i.e., sleep) and moderators (e.g., gender) on the direction and strength of associations.

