Our analysis plan has proposed an intent-to-treat analysis where all participants, regardless of whether they complete all sessions, will be invited to return for follow-up assessments. However, there will likely be some participants that refuse to return for follow-up assessments or miss a mid-point assessment. "Lost to follow up" will be defined here as missing data that is contributing to the primary outcomes. The reason will be recorded (i.e., missed visit due to traveling, illness). These criteria and documentation will also be applied for any discontinued subjects with the reasons for discontinuation being recorded (i.e., moving out of state).

Regarding the analytical approach, we propose to use all available data in the planned analysis for testing our primary outcome. Since we are examining changes over time we will be able to conduct the analysis as long as there is at

least one follow-up assessment (either at the 6-month time point or the 12-month time point). We will assess the missingness of data consistent with the assumptions of the modeling approach described above. That is, we will examine the randomness of missing data and determine if the data is missing completely at random (MCAR) or missing at random (MAR) and use maximum likelihood estimation for computation of unbiased parameters estimates and standard errors. We will not conduct multiple imputation to correct for missing data.

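### Section 1.4.1 claims 80% power for brain volume at d = 0.30 with 60 per group; the convention that reproduces the amendment's 68-83% gives 37%, and no stated assumption closes the gap

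*Combined protocol and SAP*

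**What the plan says.** Section 1.4.1 (POWER) works with 60 per group, that is, 75 per group less 20% attrition. For brain volume it reports the group's own interventions as having "moderate-sized effects (Cohen's d) ranging between 0.30 and 0.50" and cross-sectional research as having "slightly larger effect sizes between 0.50 - 0.60". It then asserts that a "conservative effect size of 0.30, 60 participants per group is sufficient to detect differences in brain volume at 80% power".

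The same section makes two other imaging claims. For diffusion imaging: "Based on an estimated effect size of 0.75, we should have 90% power with 60 participants per group". For connectivity, with d = 1.5, it says that "similar to the effect sizes and power for the other neuroimaging measures, 60 participants per group should be sufficient", at 95% power. In general terms it credits randomised trials with "increased power obtained through the within-subject analytical approach". No correlation or variance component is given.

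Section 1.4.3 (PRIMARY OUTCOMES) states that "the primary endpoints will be 12-month change scores resulting from three different measurements: (1) hippocampal volume", tested as a time-by-group interaction in a mixed model.

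The Amendments in Study Protocol reduce the target from 150 to 120. They take d = 0.5-0.6 as the effect of an exercise intervention on brain volume, citing a grant application, and give 68-83% power for hippocampal volume change allowing for 20% attrition. They conclude that power for the primary aims is sufficient. The amendment too gives no alpha, sidedness, scale of d or correlation.

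**The concern.** The two power statements concern the same kind of outcome but point in opposite directions. Section 1.4.1 has a smaller effect (0.30) reaching 80% with 60 per group. The amendment has an effect about twice as large (0.5-0.6) reaching only 68-83% with 48 per group. A 20% fall in sample size cannot offset a near-doubling of the effect if d means the same thing in both places.

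The labels on the effect sizes also differ. The 0.5-0.6 that the amendment attributes to an intervention matches the range 1.4.1 attributes to cross-sectional studies; for interventions 1.4.1 gives 0.30-0.50.

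Hippocampal volume is the first-listed primary endpoint. A reader of 1.4.1 would conclude that an effect of 0.30 is well covered, and could read a null result as evidence against such an effect. The judgement that 120 participants are enough depends on 0.5-0.6 being the intervention effect, and on the scale it is expressed in.

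**Working it through.** **Inputs.** d = 0.30, 60 per group, stated power 80% (1.4.1). d = 0.5-0.6, 120 randomised, 20% attrition, stated power 68-83% (amendment): 120 × 0.8 = 96, or 48 per group. Equal allocation (1.6). The only significance level in the plan is .01, for mediation, so two-sided 0.05 is an assumption.

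**Formula.** Two-sample t-test with n per group: noncentrality δ = d·√(n/2), df = 2n − 2; power is the noncentral-t probability beyond the critical value.

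**Step 1: reproduce the amendment.** n = 48, two-sided 0.05, d in SDs of the analysed change:
- d = 0.5: 67.9%
- d = 0.6: 82.9%
- d = 0.58: 80.3%, which fits the amendment's claim of more than 80% for cardiovascular biomarkers (d from 0.58 to 0.6)

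One-sided 0.05 gives 78% and 90%, which does not match. The two-sided convention reproduces both ends of 68-83%, and change-SD units suit a change-score endpoint.

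**Step 2: apply it to section 1.4.1.** n = 60, d = 0.30: δ = 0.30 × √30 = 1.643 against a critical value of 1.980. Power is **37.1%**.
- One-sided 0.05: 49.6%
- All 75 per group, two-sided, no attrition: about 45%
- Needed for 80% at d = 0.30: 175.4, so 176 per group (138.1 one-sided, so 139)

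The other imaging claims hold as lower bounds: d = 0.75 gives 98% against a stated 90%, and d = 1.5 gives over 99.9% against 95%.

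**Step 3: what would make 80% true?** With n = 60, 80% two-sided needs an effective d of 0.516, a gain of 0.516/0.30 = 1.719.
- d in baseline-SD units, change score: effective d = d/√(2(1−r)), so r = 0.831.
- d in baseline-SD units, baseline-adjusted: effective d = d/√(1−r²), so r = 0.813.
- One-sided versions: r = 0.784 and 0.754.
- Group-by-time F test with f = d/2 and λ = f²·N·m/(1−ρ), N = 120: ρ = 0.323 with two waves (m = 2), 0.170 with three (m = 3).

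**Step 4: apply those routes to the amendment.** At 48 per group, d = 0.5 and 0.6:
- Baseline-SD routes: 98.6% and 99.9% (two-sided); 98.0% and 99.7% (one-sided)
- F test, two waves: 98.6% and 99.9%; three waves: 99.0% and 99.9%
- F test even at ρ = 0: 92.9% and 98.4% (two waves), 97.2% and 99.7% (three waves)

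None returns 68-83%.

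**Step 5: different scales in the two places.** If 1.4.1 uses baseline-SD units with r = 0.83 and the amendment uses change-SD units, both power figures can hold, since 0.30 × 1.719 = 0.516. But then the amendment's 0.5-0.6 is only 0.29-0.35 on the scale of 1.4.1 (0.5/1.719, 0.6/1.719), and the 0.30-0.50 of 1.4.1 becomes 0.52-0.86 on the amendment's scale.

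**Step 6: power at N = 120 on the amendment's convention.** Section 1.8.3 keeps anyone with at "least one follow-up assessment (either at the 6-month time point or the 12-month time point", so 48 per group (20% lost) and 60 per group (none lost) bracket the analysed number, provided loss stays within 20%.

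| d | 48 per group | 60 per group |
|---|---|---|
| 0.30 | 31% | 37% |
| 0.40 | 49% | 58% |
| 0.50 | 68% | 78% |
| 0.60 | 83% | 90% |

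Detectable d at 80% power: 0.58 with 48 per group, 0.52 with 60.

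**The case against.** The strongest reply is that this is missing information and not a wrong sum. Section 1.4.1 declares no convention, so the 37% is computed on one inferred from a later text that itself names mixed-effects modelling. Section 1.4.1 appeals to a within-subject gain, the test is a time-by-group interaction, and the group-by-time route reaches 80% with a correlation of only 0.17 to 0.32. A high baseline-to-follow-up correlation would also do it. This stands in part: the documents cannot show that 80% is impossible, and the working does not claim so. But they do not supply the correlation or scale that would make it true, and every route tried takes the amendment's figure to 93% or above.

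Second, 60 per group belongs to the earlier target of 150, and the amendment openly reports power below 80% at its lower end. True, but 1.4.1 still stands in the protocol, and the amendment does not correct its claim about 0.30.

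Third, the amendment's 0.5-0.6 is credited to a grant application outside the documents, so borrowing from the cross-sectional range is not proven. That is fair. The labels nevertheless conflict and need reconciling.

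Fourth, attrition is reported below 10% among participants not disrupted by COVID. At 54 per group (10% lost), d = 0.5-0.6 has 73-87% power. That lies inside the 48-60 bracket and leaves d = 0.30 at 34%.

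**Conclusion.** The statement is wrong as written. Assuming two-sided 0.05 and d in SDs of the analysed change, which is the convention that reproduces the amendment, power at d = 0.30 with 60 per group is 37% against a stated 80%. The 80% survives only with a scale and correlation that the plan does not give. No single convention tested supports both power statements, so they are inconsistent or rest on different undeclared scales.

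On the amendment's convention, the intervention range of 0.30-0.50 in 1.4.1 has 31-68% power at 48 per group and 37-78% at 60. The detectable effect at 80% power, 0.52-0.58, lies above that whole range. The claim of adequate power for hippocampal volume at N = 120 is therefore conditional on 0.5-0.6 being the intervention effect in change-SD units. This must be corrected.

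**What to change.** 1. State one convention for the power calculations (alpha, sidedness, the SD that defines d, and any assumed within-subject correlation with its source) and use it in both section 1.4.1 and the amendment.
2. In 1.4.1, either replace 80% with about 37% on the amendment's convention, or document the scale and correlation that justify 80% and re-express the amendment's effect sizes and power on that scale.
3. Give the source of 0.5-0.6 and reconcile it with the 0.30-0.50 for interventions and 0.50-0.60 for cross-sectional studies.
4. In the amended statement, show power at 48 per group for 0.30-0.50 (31-68%) beside 0.5-0.6 (68-83%), or give the detectable d of about 0.58, and qualify the conclusion of adequate power for hippocampal volume accordingly.

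The cost is revised text and a less favourable power figure. No participants are added, and neither endpoint nor analysis changes.
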